Descriptive statistics will be produced for all relevant study measures, for the 2 therapy cohorts. Stabilized inverse probability treatment weighting (IPTW) will be used to balance patient characteristics between apixaban and LMWH cohorts. Post-IPTW, comparisons will be conducted using weighted chi-square tests for categorical variables and weighted t-tests (mean) for continuous variables. Comparisons between independent samples (e.g., among patients with ≥ 1 hospitalization) and pre-IPTW samples will be conducted using the parametric t-test (mean) and non-parametric Wilcoxon rank-sum test (median) for continuous variables. A p value of ≤ 0.05 will be considered significant.

Up to 4 regression models will be developed and these may include weighted generalized linear models (GLM) with log transformation and gamma distribution to estimate adjusted (all-cause) cost ratio between the two cohorts or a negative binomial distribution may be developed to estimate adjusted visits such as physician office visits, emergency room visits or other HCRU.

Milestones

Protocol and table shells: 12 August 2022

Start of data analysis: 15 August 2022

PFIZER CONFIDENTIAL

CT24-WI-GL02-RF02 4.0 Non-Interventional Study Protocol Template For Secondary Data Collection Study 01-Jun-2022

Page 10 of 35

090177e19b7d94e0\Approved\Approved On: 29-Aug-2023 01:40 (GMT)

Apixaban

B0661183 NON-INTERVENTIONAL STUDY PROTOCOL

Protocol Version: 2.0 29 July 2022

Final results: 21 October 2022

Final study reports and presentation: 18 November 2022

090177e19b7d94e0\Approved\Approved On: 29-Aug-2023 01:40 (GMT)

PFIZER CONFIDENTIAL

CT24-WI-GL02-RF02 4.0 Non-Interventional Study Protocol Template For Secondary Data Collection Study 01-Jun-2022

Page 11 of 35

Apixaban
B0661183 NON-INTERVENTIONAL STUDY PROTOCOL
Protocol Version: 2.0 29 July 2022

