9.5. Study size

An earlier feasibility study estimated that there were 4,972 VTE patients with cancer with evidence of apixaban in PharMetrics® Plus. These counts were for informational purposes only and will not represent the actual number of patients to be utilized in the study. Application of other inclusion and exclusion criteria or other factors will reduce the sample size.

Sample size calculation was conducted to identify minimum number of patients in each cohort required for the analysis using the recurrent VTE event rates from Cohen et al.^{Error! Bookmark not defined.} and Agnelli et al.^{Error! Bookmark not defined.} to achieve a power of 80% at a 5% level of significance (two-sided). Using recurrent VTE rates 4.362% (148 recurrent VTE cases in 3,393 patients) in apixaban cohort and 6.483% (396 recurrent VTE cases in 6,108 patients) in LMWH cohort from Cohen et al., we require a minimum sample of 1,788 patients in each cohort to achieve 80% power. A minimum sample of 1,867 patients in each cohort is required to achieve 80% power at a 5% level of significance (two-sided) using recurrent VTE event rates from Agnelli et al. of 5.6% in apixaban cohort and 7.9% in dalteparin cohort. Based on the sample size calculations, for the current study we need a minimum sample in the range of 1,788-1,867 patients in each cohort.

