9.7. Data analysis

Descriptive statistics will be produced for all relevant study measures previously described, for the 2 therapy cohorts of interest. Categorical measures will be presented using frequency (number of patients [n]) and percentage (%) of total study patients observed in each category. Continuous and count variables will be presented as the mean, SD, median and IQR. As relevant, continuous variables will also be categorized into intervals.

Stabilized IPTW will be used to balance patient characteristics between apixaban and LMWH cohorts.^{11,12} Weights will be constructed by estimating each subject's probability of receiving treatment based on covariates. For comparisons of baseline characteristics between the apixaban and LMWH cohorts, both pre- and post-IPTW, standardized mean difference (SMD) will be calculated to evaluate the difference in baseline covariates between cohorts. SMD is calculated as the difference in means or proportions of a variable divided by the pooled standard deviation. SMD of ≥ 0.10 between groups is considered meaningful.¹³ For comparisons of events and HCRU/cost over the variable post-index period post-IPTW, comparisons will be conducted using weighted chi-square tests for categorical variables and weighted t-tests (mean) for continuous variables (note there is no corresponding weighted test for the median). Comparisons between independent samples (e.g., among patients with ≥ 1 hospitalization) and pre-IPTW samples will be conducted using the parametric t-test (mean) and non-parametric Wilcoxon rank-sum test (median) for continuous variables; data will be reported for the unweighted sample. A p-value < 0.05 will be considered statistically significant. However, to account for multiple comparisons, a Bonferroni correction may be implemented such that the critical p-value ($p < .05$) may be divided by the number of comparisons (i.e., 3 comparisons, in order to yield a new critical p-value, $.05/3 = 0.0167$). Analyses will be conducted using SAS[®] (statistical analysis software) Release 9.4 (SAS Institute Inc., Cary, NC).

IQVIA will develop up to 4 multivariable analysis models, to be mutually agreed upon Pfizer/BMS and IQVIA. For example these may include weighted generalized linear models (GLM) with log transformation and gamma distribution to estimate adjusted (all-cause) cost ratio

PFIZER CONFIDENTIAL

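### Section 9.7 names weighted t-tests and weighted chi-square tests after IPTW but no variance estimator that accounts for the weights, so the nominal 5% level is not assured

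*Combined protocol and SAP*

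**What the plan says.** Section 9.7 states that "Stabilized IPTW will be used to balance patient characteristics between apixaban and LMWH cohorts" and that "Weights will be constructed by estimating each subject's probability of receiving treatment based on covariates". For post-index events, HCRU and costs after weighting, "comparisons will be conducted using weighted chi-square tests for categorical variables and weighted t-tests (mean) for continuous variables". The data analysis part of the abstract (section 4) repeats this, with "weighted t-tests (mean) for continuous variables". A side note in 9.7 adds that no equivalent weighted test exists for medians.

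The significance rule is "A p-value < 0.05 will be considered statistically significant". On multiplicity, "a Bonferroni correction may be implemented such that the critical p-value" is divided by the number of comparisons, with 0.05/3 = 0.0167 as the worked case.

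For regression, 9.7 allows up to four models: "For example these may include weighted generalized linear models (GLM) with log transformation and gamma distribution". It also plans two-part models for HCRU and costs related to recurrent VTE, major bleeding and CRNM bleeding. SAS 9.4 is named, but no procedure. Neither 9.7 nor the abstract gives a variance estimator for weighted quantities, a weight truncation rule or a summary of the weights. Outcomes in 9.3.2 and 9.3.3 are described by mean, SD, median and IQR, without confidence intervals.

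**The concern.** A weighted t-test or chi-square in its ordinary form takes the weights as frequencies or precisions. Stabilized weights sum to roughly the number of patients, so the standard error is computed as if every patient carried full information. Unequal weights reduce that information, and an ordinary weighted test does not register the loss. The weights are also estimated from the same data, which affects the variance in a different way and often in the opposite direction.

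The all-cause cost comparison is a primary objective, and the weighted t-test is the only analysis of it that 9.7 firmly commits to; the cost GLM is offered as an example. Two programmers could each follow 9.7 faithfully and report different p-values for that objective, one with a naive and one with a design-based standard error. The same gap carries into the models.

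**Working it through.** **1. The plan's own size calculation.** Section 9.5 sizes the study "to achieve a power of 80% at a 5% level of significance (two-sided") on recurrent VTE. For two proportions with pooled variance under the null, per cohort:

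n = [1.960·√(2p̄(1−p̄)) + 0.842·√(p₁(1−p₁)+p₂(1−p₂))]² / (p₁−p₂)²

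- 5.6% vs 7.9%: n = 1,866.6, so 1,867. This matches.
- 148/3,393 vs 396/6,108: n = 1,787.8, so 1,788. This matches.

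Both are unweighted comparisons, with no allowance for the precision lost through weighting.

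**2. Ordinary weighted test, analytic approximation.** Let the design effect be D = 1 + CV² of the weights. The documents do not give it, so the values below are assumptions. If the weights are known and unrelated to the outcome, the naive standard error is 1/√D of the true one, and type I error = 2·[1 − Φ(z/√D)], with z = 1.960 at 0.05 and z = 2.394 at 0.0167.

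| D | naive SE / true SE | type I error at 0.05 | type I error at 0.0167 |
|---|---|---|---|
| 1.05 | 0.976 | 5.6% | 1.9% |
| 1.2 | 0.913 | 7.4% | 2.9% |
| 1.5 | 0.816 | 11.0% | 5.1% |
| 2.0 | 0.707 | 16.6% | 9.0% |

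The optional Bonferroni step does not repair the error. At D = 1.5 each comparison tested at 0.0167 has an actual level of about 5%.

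**3. Simulation with an estimated propensity score.** The approximation ignores both the estimation of the weights and any link between covariates and outcome. A simulation with no treatment effect allowed for both: 3,734 patients (2 × 1,867), five covariates, logistic propensity score, stabilized weights, 1,500 to 2,000 runs per setting. The Monte Carlo standard error near 5% is about 0.5 to 0.6 points. *Naive* uses the weights as precision or frequency weights; *sandwich* is a robust variance that treats the weights as known.

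| Outcome | D | naive type I error | sandwich type I error |
|---|---|---|---|
| Skewed cost | 1.02 | about 5% | 4–6% |
| Skewed cost | 1.16 | 7–9% | 4–6% |
| Skewed cost | 1.32 | 9–13% | 4–6% |
| Skewed cost | about 1.9 | 17–27% | 4–9% |
| Binary, near 6–7% | 1.02 | about 4% | about 4% |
| Binary, near 6–7% | 1.32 | about 9% | 4–5% |
| Binary, near 6–7% | about 1.9 | 16–19% | 4–6% |
| Continuous, R² 0.3 | 1.02 | 1.5% | 1.3% |
| Continuous, R² 0.3 | 1.32 | 6.2% | 2.0% |
| Continuous, R² 0.5 | 1.07 | 0.6% | 0.2% |
| Continuous, R² 0.5 | 1.32 | 3.5% | 0.6% |

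R² is the share of outcome variance explained by the covariates in the propensity score. The sandwich result at the top of its range for skewed cost (8.7%) came from the single most extreme setting.

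Two things follow. With skewed costs or rare events, the naive test is anti-conservative once the weights spread. With strongly prognostic covariates it can be conservative, and the sandwich with known weights is then more conservative still.

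**4. Consequence for study size.** With a variance that reflects the weights, each cohort's effective size is n/D. At the planned 1,867 or 1,788, power for recurrent VTE falls from 80% to about 76% at D = 1.10, 63% at D = 1.5 and 51% at D = 2.0. To keep 80%, D = 1.5 would need 1,867 × 1.5 = 2,801 (rounded up) or 1,788 × 1.5 = 2,682 per cohort.

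**The case against.** The strongest reply is that 9.7 never says the tests are naive. A survey-weighted mean comparison and a Rao-Scott test can fairly be called a weighted t-test and a weighted chi-square, and both can be run in the SAS release named. That is correct: the defect is an unstated variance, not a stated wrong one. It does not dispose of the point. The plan names particular tests, and its note that no weighted test exists for medians reads more like standard tests run with a weight option than like a design-based analysis. Nothing in the text steers the analyst away from the ordinary form.

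A second reply is that direction and size are unknown. This also stands. With weights near 1 nothing much happens, and with strongly prognostic covariates the naive p-values can be too large. A reader might infer that the p-values are certainly too small, but the documents give neither the weight spread nor the prognostic strength that would settle it. Weights near 1 cannot be assumed either: 9.3.1 lists dozens of baseline variables, 9.7 does not say which enter the propensity model, and no truncation is planned.

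A third reply concerns reach. A reader might infer that these tests alone decide both primary objectives. The documents do not support that. Section 9.3 evaluates economic outcomes after both IPTW and GLM adjustment, and 9.7 commits to two-part models for event-related costs. Some subgroup comparisons, such as those among patients with a hospitalization, are unweighted. The models, however, have no stated variance either.

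Finally, the two methodological references cited for the weighting, and the separate table shells, might contain a variance method. The references are attached to the balancing sentence, not to the tests, and neither source is available here. They argue against asserting that a naive variance will be used, but they do not specify another.

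**Conclusion.** The point holds as an omission with real consequences. Section 9.7 names weighted tests and models on estimated weights and leaves out the variance that makes their p-values valid. Under the ordinary form, type I error is about 7%, 11% and 17% at design effects of 1.2, 1.5 and 2.0, close to 5% when weights are nearly constant, and possibly below 5% when covariates strongly predict the outcome. The design effects and simulation settings are assumptions; the plan provides nothing from which to derive the study's own values. The documents do not support the stronger claims that a naive variance is prescribed or that every p-value will be too small. It should be corrected before analysis, because the remedy is inexpensive and a primary cost comparison depends on it.

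**What to change.** In 9.7, and briefly in the abstract, state that all weighted comparisons and weighted models use a variance that accounts for the weights. Either of these would do:

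- a design-based variance: survey-weighted comparison of means, Rao-Scott chi-square, or weighted regression with sandwich standard errors, applied also to the weighted GLM and to the two-part models where they are weighted;
- preferably, a bootstrap of patients that re-estimates the propensity score and the weights in each resample, because a sandwich that treats the weights as known can be conservative.

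Report 95% confidence intervals with every weighted comparison, together with the weight distribution and the effective sample size in each cohort. Set that effective size against the 1,788–1,867 per cohort in 9.5.

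The design-based option takes a sentence or two and uses procedures available in the named SAS release. Intervals will usually be somewhat wider. The bootstrap costs additional programming and computing time, most of all for the two-part models and any stepwise covariate selection. No new data are needed.

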9.3. Variables

Unadjusted subject demographic and clinical characteristics and select HCRU and cost characteristics will be described for subjects in the apixaban and LMWH cohorts. Stabilized inverse probability of treatment weighting (IPTW) will be used to adjust for imbalances in measured confounders between the two therapy cohorts. Subject characteristics will then be reported for the therapy cohorts post-IPTW. Post-index economic outcomes of interest (i.e., HCRU and costs) will be evaluated following both IPTW and GLM adjustment.

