9.3.2. All-cause HCRU and Costs Over the Post-Index Period (Post-IPTW)

All-cause HCRU and costs will be reported for the Apixaban and LMWH cohorts over the variable post-index period (minimum 1 month enrollment), post-IPTW. Costs will be reported

PFIZER CONFIDENTIAL

CT24-WI-GL02-RF02 4.0 Non-Interventional Study Protocol Template For Secondary Data Collection Study 01-Jun-2022

Page 23 of 35

090177e19b7d94e0\Approved\Approved On: 29-Aug-2023 01:40 (GMT)

Apixaban

B0661183 NON-INTERVENTIONAL STUDY PROTOCOL

Protocol Version: 2.0 29 July 2022

as per patient per month (PPPM). Over the post-index period, a 30 day period will be used (to represent a month) to ‘standardize’ the period of time for which costs and HCRU will be reported. For each patient, costs will be divided by the variable post-index period in total-person days and then multiplied by 30 to calculate PPPM costs. For example, if a patient has total costs of \$10,000 with 60 days of follow-up, the PPPM will be calculated as $(\$10,000/60) * 30 = \$5,000$.

HCRU will be expressed as both the proportion of patients with such utilization (e.g., the percentage of patients with at least one pharmacy claim, the percentage of patients with at least one physician office visits, etc.) as well as per-patient mean, SD, median and IQR number of visits/services. Costs will be expressed as per-patient mean, SD, median and IQR. Utilization and costs will be calculated on a per patient basis, averaged across the cohort. The denominator will include all patients in the cohort. Costs will be converted to 2021 US dollars (USD) using the medical component of the Consumer Price Index.

HCRU and costs will be reported for mutually exclusive categories: outpatient pharmacy, inpatient hospitalizations, and outpatient care. Outpatient care will comprise the following categories: ER visits, outpatient physician office visits, outpatient surgical visits, laboratory and pathology, radiology and all other services.

All-cause HCRU and costs will be reported for each of the following services:

- Pharmacy
 - Patients with ≥ 1 prescription fill (n, %)
 - Number of prescription fills per patient (mean, SD, median, IQR)
 - Total pharmacy cost per patient (mean, SD, median, IQR)
- Outpatient Services
 - Total outpatient medical care cost per patient (mean, SD, median, IQR)
 - Physician office visits
 - Patients with ≥ 1 physician office visit (n, %)
 - Number of physician office visits per patient (mean, SD, median, IQR)

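### Section 9.7 tests post-index subsets, such as hospitalised patients, without the IPTW weights, which leaves measured confounding in those p-values and conflicts with sections 9.3, 9.3.2 and 9.3.3

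*Combined protocol and SAP*

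**What the plan says.** Section 9.7 sets out the confounding control: "Stabilized IPTW will be used to balance patient characteristics between apixaban and LMWH cohorts". For events, resource use and costs over the follow-up period it prescribes "weighted chi-square tests for categorical variables and weighted t-tests (mean) for continuous variables", and adds in brackets: "note there is no corresponding weighted test for the median".

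The next sentence sets a different rule: "Comparisons between independent samples (e.g., among patients with ≥ 1 hospitalization) and pre-IPTW samples will be conducted using the parametric t-test (mean"), with the Wilcoxon rank-sum test for medians, and then "data will be reported for the unweighted sample". Post-index subsets and pre-IPTW samples thus get the same treatment. No covariate adjustment is attached to these tests. The threshold is p < 0.05, with a Bonferroni correction only optional. The abstract repeats the choice of tests but not the clause on unweighted data.

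Other sections point the other way:
- Section 9.3: "Post-index economic outcomes of interest (i.e., HCRU and costs) will be evaluated following both IPTW and GLM adjustment".
- Section 9.3.2 carries Post-IPTW in its heading and states: "The denominator will include all patients in the cohort". Length of stay is listed there.
- Section 9.3.3 introduces its list of recurrent VTE and bleeding outcomes as post-IPTW. Days from index to first event are on that list.

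**The concern.** The cohorts are not randomised, and the plan relies on weighting to make them comparable. A t-test or Wilcoxon test among hospitalised patients without weights compares groups that may still differ on the factors the weights were built to balance. A small p-value could reflect those differences alone.

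The report could then show weighted and unweighted p-values for the same family of outcomes, judged against the same threshold. An analyst also could not tell which rule governs an outcome that exists only in patients with an event. Time to first event is the clear case: section 9.3.3 implies weighting, and the subset rule in 9.7 implies none.

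The only reason given nearby is the absence of a weighted test for the median. That would not explain removing the weights from a comparison of means, and it is inaccurate: weighted quantile regression and design-based rank tests are available. Calling the subsets independent samples does not help either. The two cohorts are independent groups with or without weights, and each patient in a subset keeps a weight.

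**Working it through.** **1. The plan's own figure.** Section 9.5 gives 1,788 to 1,867 patients per cohort. With the pooled-variance formula for two proportions, 1:1, two-sided 5%, 80% power and no continuity correction, 148/3,393 against 396/6,108 gives 1,788, and 5.6% against 7.9% gives 1,867. Both reproduce. They serve here only to set a plausible study size: 2 × 1,788 = 3,576.

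**2. The sections side by side.**

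| Outcome | Sections 9.3 to 9.3.3 | Section 9.7 |
|---|---|---|
| Whole-cohort costs and resource use | after IPTW, all patients in the denominator | weighted tests: consistent |
| Length of stay | under the Post-IPTW heading, all patients in the denominator | weighted if averaged over all patients; unweighted if restricted to hospitalised patients |
| Time to first event | listed as post-IPTW | defined only in patients with an event, so the subset rule points to unweighted |
| Any comparison among patients with at least one hospitalization | after IPTW and GLM as a general statement | unweighted t-test and Wilcoxon |

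**3. Approximate size.** None of these inputs is in the documents.
- Hospitalised share 30%: 0.30 × 1,788 ≈ 536 per cohort.
- One measured confounder with standardized mean difference (SMD) 0.2 to 0.3 before weighting, correlated 0.3 with an outcome of SD 1.
- No true treatment effect.

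Bias = SMD × correlation = 0.2 × 0.3 = 0.06 SD to 0.3 × 0.3 = 0.09 SD.
SE = √(2/536) = 0.061 SD.
Shift = 0.06/0.061 = 0.98 to 0.09/0.061 = 1.47 standard errors.
Type I error = P(|Z + shift| > 1.96) ≈ 17% to 31%.

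By the same formula, for a given bias:

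| Patients per cohort in the subset | Bias 0.05 SD | Bias 0.10 SD |
|---|---|---|
| 357 (20%) | 10.2% | 26.7% |
| 536 (30%) | 13.0% | 37.4% |
| 715 (40%) | 15.7% | 47.2% |

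**4. Simulation with and without weights.** 3,576 patients, about 30% hospitalised, no treatment effect on outcome or hospitalisation, one measured confounder that mildly raises hospitalisation, 1,500 runs. Ranges are for outcome correlation 0.2 to 0.3.

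| Confounder SMD (about) | Unweighted type I error | Weighted (all settings) |
|---|---|---|
| 0.1 | 5.8-8.7% | 4.2-6.2% |
| 0.2 | 9.8-17.2% | 4.2-6.2% |
| 0.3 | 14.9-27.9% | 4.2-6.2% |

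At correlation 0.3 the simulated biases were 0.058 and 0.085 SD, slightly below the 0.06 and 0.09 of step 3. A variant in which the confounder has more influence on hospitalisation lowers the bottom of the range, so about 14-28% covers the runs at correlation 0.3 and SMD 0.2 to 0.3. Section 9.7 itself treats an SMD of 0.10 or more as meaningful.

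**5. When treatment affects hospitalisation.** The subset is defined after index, so baseline weights no longer guarantee balance inside it. With correlation 0.3 and no direct treatment effect on the outcome:
- SMD 0.2, log-odds on hospitalisation 0.8 for treatment and 1.0 for the confounder: 4.6% unweighted, 10.8% weighted.
- SMD 0.1, log-odds 0.5 and 1.0: 5.8% unweighted, 9.0% weighted.
- Where selection and confounding push in the same direction, weighting lowers the error from about 31% to about 10%, still above 5%.

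**The case against.** The strongest reply is that little of the study depends on this sentence. The whole-cohort cost comparisons that serve the primary objectives are weighted. For event-related resource use or costs, section 9.7 commits to two-part models, whose second part is an adjusted comparison among patients with a positive value. The subset rule rests on one example in brackets, and no outcome in 9.3.2 or 9.3.3 is expressly confined to hospitalised patients. Section 9.3 can be read as a general statement to which 9.7 makes an exception.

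Most of this stands as a limit on scope, and it rules out three stronger readings.
- A reader might infer that length of stay and time to first event would be compared with no confounding control. The documents do not say so. Length of stay sits under a Post-IPTW heading with all patients in the denominator, and time to first event is listed as post-IPTW. For the latter, 9.3.3 and 9.7 disagree; neither settles it.
- A reader might infer that the primary cost results are unadjusted. They are not.
- A reader might infer that dropping the weights is always worse. Step 5 of the working shows that it is not: when selection and confounding offset each other, the unweighted test can be closer to its nominal level.

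The reply does not rescue the unweighted p-values. The two-part models cover event-related outcomes only and do not replace the subset tests. The all-cause GLM is an example of what may be fitted within a limit of four models. An exception that removes confounding control needs a reason, and the note on medians does not supply one.

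**Conclusion.** The point holds in a limited form and is minor. Section 9.7 states an explicit rule that tests post-index subsets unweighted and unadjusted at p < 0.05. That leaves measured baseline confounding in those p-values and conflicts with sections 9.3, 9.3.2 and 9.3.3. The reason given is inaccurate for medians and irrelevant to means.

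The type I error of about 14-28% unweighted against about 5% weighted is an illustration. It rests on an assumed hospitalised share, SMD and correlation, one measured confounder, and no treatment effect on hospitalisation. Without that last assumption the benefit of weighting varies and can reverse. Weights alone therefore do not make a subset p-value trustworthy, and subset results should carry no significance claim in either form.

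**What to change.** In section 9.7:
1. Limit unweighted t-tests and Wilcoxon tests to pre-IPTW tables.
2. Report post-index subset results with each patient's stabilized weight and a robust or bootstrap variance. For medians, use weighted quantile regression or a design-based rank method.
3. Label these results descriptive, without significance claims, because the subset is defined after index and the weights do not remove the resulting selection bias.
4. Correct the note that no weighted test for the median exists.
5. Reconcile 9.7 with 9.3, 9.3.2 and 9.3.3. For length of stay and time to first event, state the denominator and whether weights apply. Align the abstract.

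The weights are already planned, so the change is a few sentences of text and little programming. The price is slightly wider intervals and no significance claims for subset results. No stated sample size changes.

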8. RESEARCH QUESTION AND OBJECTIVES

The purpose of this study is to evaluate the costs and HCRU associated with treating VTE cancer patients with apixaban compared to LMWH (dalteparin, enoxaparin, or tinzaparin).

The objectives of the study are as follows:

Primary objectives:

- To compare all-cause healthcare costs among VTE patients with cancer treated with apixaban vs LMWH
- To compare costs associated with recurrent VTE, major bleeding, and clinically relevant non-major (CRNM) bleeding among VTE patients with cancer treated with apixaban vs LMWH

Secondary objectives:

- To compare all-cause HCRU among VTE patients with cancer treated with apixaban vs LMWH
- To compare HCRU associated with recurrent VTE, major bleeding, and CRNM bleeding among VTE patients with cancer treated with apixaban vs LMWH

090177e19b7d94e0\Approved\Approved On: 29-Aug-2023 01:40 (GMT)

PFIZER CONFIDENTIAL

CT24-WI-GL02-RF02 4.0 Non-Interventional Study Protocol Template For Secondary Data Collection Study 01-Jun-2022

Page 15 of 35

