CT24-WI-GL02-RF02 4.0 Non-Interventional Study Protocol Template For Secondary Data Collection Study 01-Jun-2022

Page 26 of 35

090177e19b7d94e0\Approved\Approved On: 29-Aug-2023 01:40 (GMT)

Apixaban

B0661183 NON-INTERVENTIONAL STUDY PROTOCOL

Protocol Version: 2.0 29 July 2022

- Number of CRNM bleeding events (denoted by inpatient or outpatient events that meet the definition above) (mean, median, SD, IQR)
- Time (in days) from index date to first CRNM bleeding event (mean, median, SD, IQR)

The Cost, and HCRU, for each event will be defined as the cost associated with the hospitalization for the respective event (i.e., recurrent VTE, MB, or CRNM bleeding) as well as all subsequent event-related medical costs (pharmacy costs will not be included). These can be determined via an appropriate diagnosis code that relates to the event of interest. Major bleeding-related medical costs will be defined as costs associated with the first major bleeding hospitalization plus all subsequent bleeding costs occurring in the inpatient (primary or secondary diagnosis) or outpatient setting (any position). Recurrent VTE-related medical costs will be defined as the costs associated with the first recurrent VTE hospitalization plus all subsequent VTE costs in the inpatient (primary or secondary diagnosis) or outpatient (any position) setting. Similarly, CRNM bleeding-related medical costs will be defined as hospitalization costs or outpatient costs associated with the first CRNM bleeding as defined above and all the subsequent CRNM bleeding costs in the inpatient (primary or secondary diagnosis) or outpatient (any position) setting.

The outpatient services and inpatient hospitalization HCRU and cost variables presented in section 8.3.2 will also be reported for recurrent VTE-related, major bleeding-related and CRNM bleeding-related utilization and costs.

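### Section 9.7 lets about 112 HCRU, event and cost-component comparisons be called significant at p<0.05, with no testing order or exploratory label and only an optional Bonferroni step for three unnamed comparisons

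*Combined protocol and SAP*

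**What the plan says.** Section 9.7 sets the tests for the post-index measures: "For comparisons of events and HCRU/cost over the variable post-index period post-IPTW, comparisons will be conducted using weighted chi-square tests for categorical variables". Means of continuous variables are compared by t-test, also weighted. It then gives one threshold without restricting it to any tier: "A p-value < 0.05 will be considered statistically significant". The abstract says "A p value of ≤ 0.05 will be considered significant".

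The next sentence of 9.7 is the only multiplicity provision: "to account for multiple comparisons, a Bonferroni correction may be implemented". It illustrates this with "3 comparisons, in order to yield a new critical p-value" of 0.0167. It does not say which three comparisons are meant, or when the decision to correct is taken. The abstract does not mention the correction.

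Section 8 has two tiers. All-cause costs and the costs of recurrent VTE, major bleeding and CRNM bleeding are primary. HCRU is secondary but is still worded as a comparison, for example "To compare all-cause HCRU among VTE patients with cancer treated with apixaban vs LMWH".

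Section 9.3.2 lists the all-cause measures. Section 9.3.3 adds event measures and says that the outpatient and inpatient lines "will also be reported for recurrent VTE-related, major bleeding-related and CRNM bleeding-related utilization and costs".

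**The concern.** The tiers in section 8 have no counterpart in section 9.7. No comparison depends on the result of another, no alpha is allocated, and no post-index comparison is called exploratory or descriptive. Read as written, a difference in laboratory tests or radiology cost at p = 0.04 has the same standing as a difference in total all-cause cost, even when total cost shows no difference.

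With this many lines, some will often cross 0.05 by chance. Because the correction is optional and its scope is undefined, it can be chosen or left out after results are known; section 12 has result tables shared with the sponsor throughout the analytic phase. At stake is whether an isolated HCRU or cost line can be reported as a study finding.

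**Working it through.** **1. The plan's own figure.** 0.05/3 = 0.01667, which rounds to the stated 0.0167. It reproduces. The protocol gives no count of tests.

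**2. Count of listed measures.** Counting rule: lines that appear twice are counted once, and the top-10 discharge diagnoses are left out.

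| Source | Items | Count |
|---|---|---|
| 9.3.2 all-cause | pharmacy 3 + total outpatient cost 1 + office, ER, laboratory, radiology and surgical 5 × 3 = 15 + ancillary/other 3 + HCPCS drug cost 1 + inpatient 5 + total cost 1 | 29 |
| 9.3.3 event-related | (outpatient 20 + inpatient 5) × 3 event types | 75 |
| 9.3.3 event occurrence | (any event, number, time to first) × 3 event types | 9 |
| Total | 29 + 75 + 9 | 113 |

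Removing total all-cause cost leaves 112. The three event-related cost totals are not separate lines in this count. Adding them and then removing all four primary totals gives 113 + 3 − 4 = 112 again.

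Of the 112, the non-cost measures are 18 all-cause + 16 × 3 event-related + 9 event occurrence = 75. This 75 is a different set from the 75 in the table. The other 37 are cost components.

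**3. Sensitivity to the counting rule.**
- For recurrent VTE and major bleeding, any event and number of hospitalizations largely repeat the inpatient lines. Merging these four gives 108.
- Testing the ten top diagnoses once gives 112 + 10 = 122.
- Testing them in all four lists gives 112 + 40 = 152.

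**4. Expected false positives.** Formula: m × α. It needs true null hypotheses and tests of correct size, but not independence.

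| m | α | Expected |
|---|---|---|
| 112 | 0.05 | 5.6 |
| 108 | 0.05 | 5.4 |
| 152 | 0.05 | 7.6 |
| 75 (non-cost only) | 0.05 | 3.75 |
| 112 | 0.05/3 | 1.9 |

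If only half or three quarters of the 112 nulls are true, the figure at 0.05 is 2.8 or 4.2.

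**5. Chance of at least one false positive.** The protocol gives no correlations, so ρ is assumed. Model: m normal test statistics with a common correlation ρ and two-sided critical value c. The probability is 1 − ∫ φ(u) [Φ((c − √ρ u)/√(1−ρ)) − Φ((−c − √ρ u)/√(1−ρ))]^m du.

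| Tests | Threshold | ρ = 0.3 | ρ = 0.5 | ρ = 0.8 |
|---|---|---|---|---|
| 112 | 0.05 | 0.957 | 0.800 | 0.369 |
| 112 | 0.0167 | 0.65 | 0.44 | 0.17 |
| 29 (all-cause list only) | 0.05 | 0.651 | 0.499 | 0.253 |
| 4 (primary costs only) | 0.05 | 0.174 | 0.156 | 0.114 |

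The last row bears on the fix. Restricting significance claims to four primary costs, each at 0.05, would still leave an 11% to 17% chance of a false claim.

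**The case against.** **The plan is not silent on multiplicity.** A reader might infer that every comparison is simply declared at 0.05. The sentence after the 0.05 rule allows a correction, and at 0.0167 on every test the expected number falls from 5.6 to 1.9. This stands as a limit on the claim. It does not remove the problem, because the step is optional, the three comparisons are unnamed, and 0.0167 on all 112 tests still leaves a 17% to 65% chance of at least one false positive. It would be too strong to say that the provision excludes the HCRU measures; its scope is undefined.

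**The tiers exist, and cost components are not secondary.** Section 8 places costs under the primary objectives and only HCRU under the secondary ones. Both points stand. What is missing is a testing rule tied to the tiers, and a statement of which cost figures are the primary ones.

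**112 is a count, not a planned number of tests.** Sections 9.3.2 and 9.3.3 say that the lines will be reported. The table shells, a separate file, would show which get a p-value, and they cannot be seen here. Section 9.7 also assigns event-related HCRU and costs to two-part regression. So 112 should be read with its rule and range. Still, the weighted tests in 9.7 are stated for post-index events, HCRU and costs in general, with no line exempted.

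**The global null is artificial and the measures overlap.** The sample size in section 9.5 assumes different recurrence rates, so some nulls are expected to be false. Any use, visit count and cost of one service move together, and a single common correlation is a crude model. A reader might infer that five or six false findings will appear, or that some are almost certain. Neither is supported. The 5.6 is an average, correlated errors come in clusters, and at ρ = 0.8 there is a 63% chance of none (1 − 0.37).

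**Conclusion.** The point holds in this form: section 9.7 gives one 0.05 rule for a long list of post-index comparisons, its only safeguard is optional and undefined in scope, and nothing below the primary costs is ordered or labelled exploratory. If no measure differed and all were tested at 0.05, the average number of false positives would be 5.6 (5.4 to 7.6 by counting rule), and the chance of at least one would be 37% to 96% over assumed correlations of 0.8 to 0.3. The count and the correlations are mine, not the protocol's. The conclusion does not depend on the exact count: the 29 all-cause measures alone give 25% to 65%.

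This is a gap in how findings may be claimed. It does not show that the primary cost comparisons are invalid, and it says nothing about which results will turn out false.

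**What to change.** In section 9.7 and the abstract:

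1. Name four primary comparisons: total all-cause cost, recurrent VTE-related cost, major bleeding-related cost and CRNM bleeding-related cost.
2. Make the Bonferroni correction binding for these four, at 0.05/4 = 0.0125, in place of the optional step for three. Keeping 0.0167 for four tests would allow up to 4 × 0.0167 = 0.067 overall.
3. Limit claims of statistical significance to these four.
4. Label the HCRU measures, event measures and cost components in 9.3.2 and 9.3.3 exploratory. Report them as weighted estimates with 95% confidence intervals, stated to be unadjusted for multiplicity, and base no study conclusion on any single one.

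The cost is a few sentences in two places, plus a check that the table shells agree. No change to data, design or sample size is needed. The downsides are a stricter threshold for the primary costs, and that a single HCRU or cost-component line can no longer be reported as significant.
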